Table 3	Adequate Organ Function Laboratory Values	23
Table 4	Trial Treatment	26
Table 5	Treatment Delay/Discontinuation Guidelines for Drug-Related Adverse Events	27
Table 6	Recommended Management Guidelines for Adverse Events Associated with Cytokine Release	33
Table 7	Management Guidelines for Infusion Reactions	36
Table 8	Laboratory Tests	48
Table 9	Tumor Response Evaluation: Comparison of RECIST 1.1 and irRECIST	52
Table 10	Best Overall Response (RECIST 1.1)	53
Table 11	Immune-Related Best Overall Response (irBOR)	54
Table 12	Attribution Categories	61

Table of Figures

No table of figures entries found.

ABBREVIATIONS

ADXS11-001	Lm -LLO Immunotherapy for HPV associated diseases
AEs	Adverse Events
APC	Antigen Presenting Cell
CD4	Cytotoxic T cell, effector T cell, Memory T cell
CD8	Helper T cell, Regulatory T cell
CAT	chloramphenicol acetyl transferase
CFU	Colony Forming Unit
CMP	Comprehensive Metabolic Panel
CR	Complete response
CRP	C-Reactive Protein
CTL	Cytotoxic T lymphocyte
DCR	Disease Control Rate
DLT	Dose limiting toxicity
DTH	delayed-type Hypersensitivity
ESR	Erythrocyte Sedimentation Rate
GLP	Good Laboratory Practice
GMP	Good Manufacturing Practice
GOG	Gynecologic Oncology Group
HPV	Human papilloma virus
HspE7	Heat Shock Fusion Protein-Based Immunotherapy
IV	Intravenously
IFN	Interferon
LFT	Liver Function Test
LLO	Listeriolysin O
Lm	Listeria monocytogenes
Lmdd	An attenuated strain of Listeria monocytogenes with deletions in two genes (dal and dat)
Lm -LLO	Listeria monocytogenes Listeriolysin O
MDSC	myeloid-derived suppressor cells
MHC	Major Histocompatibility Complex
MIC	Minimum inhibitory concentration
MMC	Mitomycin C
MTD	Maximum Tolerated Dose
NCCN	National Comprehensive Cancer Network
NSAID	Non-Steroidal Anti Inflammatory Drugs

PI3K	Phosphoinositide 3-kinase
PR	Partial response
PSA	Prostate-specific antigen
RBC	Red blood cell
RECIST	Response Evaluation Criteria in Solid Tumors
RP2D	Recommended Phase 2 Dose
SAE	Serious Adverse Event
SD	Stable Disease
SOC	Standard of Care
TAA	Tumor Associated Antigen(s)
TCR	T-cell receptor
TNF α	Tumor necrosis factor alpha
TIL	Tumor infiltrating lymphocytes
tLLO	Truncated LLO
Tregs	Regulatory T cells
wt-Lm	wild type Listeria monocytogenes

1 SUMMARY

Study Title:	Phase 2 Study of ADXS11-001 In Subjects with Persistent/Recurrent, Loco-Regional or Metastatic Squamous Cell Carcinoma of the Anorectal Canal
Trial Phase	Phase II
Clinical Indication	Persistent/recurrent, loco-regional or metastatic squamous cell carcinoma (SCCA) of the anorectal canal
Trial Type	Interventional
Study Centers	Multicenter, USA
Route of Administration	Intravenous (IV)
Trial Blinding	Open label, unblinded
Number of Trial Subjects	Approximately 55 
 • 31 subjects in Stage 1 • 24 subjects in Stage 2
Estimated Duration of Trial	Approximately 6 years
Duration of Participation	Each subject will participate in the study for an average of approximately 6 years from the time the subject signs the informed consent form (ICF) through the final contact. Treatment will continue for up to 2 years or until the subject meets a discontinuation criterion (e.g., has either documented progression, unacceptable adverse events (AEs), withdrawn due to investigator's discretion, subject withdraws consent, pregnancy, or noncompliance with study procedures or treatments). Subjects who have been on therapy for >6 months and who attain a complete response (CR) may consider stopping the trial. Subjects who achieve a CR should receive at least 1 additional cycle of treatment. The study duration includes an active study treatment phase which may last up to a maximum of 36 months and a 3 year Lm Surveillance Monitoring Phase, which includes 6 months of oral antibiotic administration to commence upon completion of the active study treatment phase or upon study discontinuation. All subjects will be followed for adverse and serious adverse events (SAEs) for a minimum of 30 days. End of Study will be defined as 1 year after the last subject is enrolled on study. However, any ongoing subject, subjects who are still deriving clinical benefit from ADXS11-001 therapy at the end of their 2 year treatment period or at the end of the study may be enrolled into a separate extension study, as available.
Randomization Ratio	None
Methodology	This is a single arm Phase 2 study. Stage 1 and 2 of the study are monotherapy evaluations of ADXS11-001 in 31 and 24 subjects, respectively with persistent/recurrent, loco-regional or metastatic SCCA of the anorectal canal that have received at least 1 regimen for the treatment of advanced disease. Additionally, those deemed by their investigator as not optimal candidates for chemotherapy would be considered eligible.

Study Title:	Phase 2 Study of ADXS11-001 In Subjects with Persistent/Recurrent, Loco-Regional or Metastatic Squamous Cell Carcinoma of the Anorectal Canal
	In addition, all subjects will participate in a 3 year Lm surveillance period. The surveillance period will begin following the last dose of study treatment or at the time of study discontinuation. This period is intended to help ensure the eradication of Lm bacteria. This period will also include a 6 month course of trimethoprim/sulfamethoxazole which will be initiated approximately 72 hours after the completion of the last dose of ADXS11-001 or immediately following study discontinuation.
Objectives	
Primary:
 
 • To evaluate efficacy as measured by the overall response rate and rate of 6 month progression-free survival (PFS) in subjects with persistent/recurrent, loco-regional or metastatic SCCA of the anorectal canal as determined by RECIST 1.1. 
Secondary:
 
 • To evaluate efficacy as measured by the overall response rate and rate of 6 month PFS in subjects with persistent/recurrent, loco-regional or metastatic SCCA of the anorectal canal as determined by irRECIST. • To evaluate the safety and tolerability of ADXS11-001 in subjects with persistent/recurrent, loco-regional or metastatic SCCA anorectal canal SCCA of the anorectal canal by NCI CTCAE 4.0 • To evaluate the additional parameters of efficacy (duration of response, PFS and overall survival) of ADXS11-001 in subjects with persistent/recurrent, loco-regional or metastatic SCCA of the anorectal canal as determined by RECIST 1.1 and irRECIST.
Criteria for Evaluation	
Safety: recorded AEs, changes in physical examinations, vital signs measurements, clinical laboratory evaluations and Lm surveillance monitoring.
 
Efficacy: Response rates as measured by RECIST 1.1 and irRECIST, duration of response, PFS

2 TRIAL DESIGN

Specific procedures to be performed during this trial, as well as the prescribed times and associated visit windows are outlined in the Schedule of Events- [Section 6.1](#). Details of each procedure are provided in [Section 7.1](#) - Trial Procedures.

This is a multi-center, open-label, 2 stage monotherapy study of ADXS11-001 in subjects with persistent/recurrent, loco-regional or metastatic SCCA of the anorectal canal that was previously treated in the metastatic setting. Stage 1 of the study will evaluate the safety and efficacy of ADXS11-001. After 31 evaluable subjects have been enrolled, further accrual will be temporarily stopped in Stage 1 to complete an interim efficacy

analysis evaluation. If the efficacy from Stage 1 demonstrates a response rate $\geq 10\%$ by either RECIST 1.1 or 6-month progression free survival (PFS) rate $\geq 20\%$, enrollment will re-open to Stage 2. Enrollment will be complete in Stage 2 when an additional 24 evaluable subjects have been accrued (total 55).

Subjects will be treated with intravenous (IV) ADXS11-001 administered over [REDACTED] every 3 weeks at a dose of 5×10^9 CFU for up to 2 years or until a discontinuation criterion is met. A treatment cycle is defined as 9 weeks. Tumor assessments will occur every 9 weeks (Week 8 of every Cycle). Subjects will be monitored for adverse events (AEs) throughout the study; AEs will be graded in severity according to the guidelines outlined in the NCI Common Toxicity Terminology Criteria for Adverse Events (CTCAE) version 4.0.

Safety follow-up will be conducted via telephone call 30 days (± 5 days) after the last ADXS11-001 infusion to confirm the resolution of any ongoing AEs and SAEs. Survival Follow-Up will be conducted at each visit during the Lm Surveillance period and via a telephone call every 3 months (± 2 weeks) after the Lm Surveillance period to determine survival status for all subjects.

The end of the study will be defined as 1 year after the last subject has enrolled on study. However, any ongoing subjects, subjects who are still deriving clinical benefit from ADXS11-001 therapy at the end of their 2-year treatment period or at the end of the study may be enrolled into a separate extension study, as available.

Safety and efficacy analysis will be performed for both parts of the study. Subject disposition, demographic and baseline characteristics will be summarized separately for Stage 1 and Stage 2. Adverse events will be classified and summarized by system organ class (SOC) and preferred term, incidence, severity, and causality. All subjects who receive at least 1 dose of study treatment will be included in the safety analyses.

Efficacy analysis will be performed for Stage 1 separately (interim analysis) and both parts of the study combined. All subjects who have completed at least 1 cycle of study treatment will be included in the efficacy analyses.

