3.2 Secondary Objectives

Objective: To evaluate efficacy as measured by the overall response rate and rate of 6 month PFS in subjects with persistent/recurrent, loco-regional or metastatic SCCA of the anorectal as determined by irRECIST

Objective: To evaluate the safety and tolerability of ADXS11-001 in subjects with persistent/recurrent, loco-regional or metastatic SCCA of the anorectal canal by NCI CTCAE 4.0.

Objective: To evaluate the additional parameters of efficacy (duration of response, PFS and overall survival) of ADXS11-001 in subjects with persistent/recurrent, loco-regional or metastatic SCCA of the anorectal canal as determined by RECIST 1.1 and irRECIST.

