7.1.6.3 Safety Follow-up/Post-Treatment Visits

Safety follow-up will be conducted via telephone call 30 days (± 5 days) after the last ADXS11-001 infusion to confirm the resolution of any ongoing AEs and SAEs. Additional unscheduled visits may be considered as needed and at the discretion of the investigator.

Surveillance monitoring for the detection of *Lm* will be initiated at the completion of study treatment according to the protocol or at the time of study discontinuation if earlier. This surveillance monitoring phase will consist of a 6 month course of oral antibiotics, obtaining a blood sample to monitor CBC, CMP, including CRP and ESR, and blood cultures at regular intervals. This testing will be performed on all subjects who have received at least one dose of ADXS11-001. It will occur every 4 months (± 2 weeks) for 3 years beginning after the last dose of study treatment. If a persistent increase in CRP and/or ESR is observed with negative blood cultures for listeria during this time the subject should be evaluated and treated, as appropriate, for another possible cause. In the event that a definite cause has not been identified then subjects must continue to be monitored closely, including another additional testing and a blood culture, for possible signs/symptoms of listeriosis. This testing may be performed at the investigative site or at another acceptable location following consultation with the Sponsor.

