7.1.6.4 Survival Follow-up

Survival Follow-Up will be conducted at each visit during the *Lm* Surveillance period and via a telephone call every 3 months (± 2 weeks) after the *Lm* Surveillance period to determine survival status for all subjects.

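### For 3 years after the last dose, survival status depends on 4-monthly Lm-surveillance visits with no contact named for subjects who miss them, so overall survival may be biased upward

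*Combined protocol and SAP*

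**What the plan says.** Section 3.2 lists overall survival among the secondary efficacy parameters: "To evaluate the additional parameters of efficacy (duration of response, PFS and overall survival) of ADXS11-001". Section 8.1 summarises time-to-event variables by Kaplan-Meier and leaves the details to a SAP. Section 8.3.1 defines PFS. The text available contains no definition of overall survival and no censoring rule for it.

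The schedule of survival contact is the same in Section 2, Section 6.1 (footnote 5) and Section 7.1.6.4. Section 2 reads "Survival Follow-Up will be conducted at each visit during the Lm Surveillance period and via a telephone call every 3 months", and the calls are placed "after the Lm Surveillance period to determine survival status for all subjects". On the start of surveillance, Section 1 says: "The surveillance period will begin following the last dose of study treatment or at the time of study discontinuation". Sections 5.6.4 and 7.1.6.3 describe it as blood tests and cultures every 4 months for 3 years. Section 7.1.6.3 adds: "This testing may be performed at the investigative site or at another acceptable location following consultation with the Sponsor".

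On the study end, Section 2 says: "The end of the study will be defined as 1 year after the last subject has enrolled on study". Section 1 repeats this definition, but also gives about 6 years for the trial, an average of about 6 years for each subject's participation, and the 3-year surveillance phase.

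**The concern.** The subjects most likely to miss a blood-draw visit are those who are too ill to attend, have declined further draws, or have died. The telephone contact that could find them is scheduled only after the 3 years in which most deaths in an advanced-disease population are likely to occur. A death that nobody learns of enters the Kaplan-Meier analysis as a censoring at the last contact. Because that censoring is related to dying, it pushes the curve up. The trial has a single arm, so no concurrent control shares the bias, and any comparison with outside survival figures would carry it in full.

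The study-end definition makes this worse. Taken at its word, it closes the study before many or all subjects reach the calls, and it cuts short the 3-year surveillance itself.

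**Working it through.** **1. Contacts after the last dose**

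- One 30-day telephone call, for adverse events (Sections 2 and 7.1.6.3).
- Surveillance visits every 4 months for 36 months: 36/4 = 9 visits, at which survival status is taken.
- Survival calls every 3 months, starting 36 months after the last dose.
- Serious adverse event reporting to 30 days after treatment. The 24-hour clause leaves out deaths from progression, and later events are reportable only if judged related to the product (Section 7.2.3.1).
- A duty to try to reach subjects who stop early or are lost, stated together with arranging end-of-therapy assessments (Section 5.8).

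A progression death 5 months after the last dose, in a subject who has stopped attending, has no stated route into the database.

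**2. Who reaches the calls before the study ends**

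Let a = months between a subject's entry and the last enrolment, and d = months from entry to last dose. Counted from that subject's entry, the calls open at d + 36 and the study ends at a + 12. The calls open in time only if d + 36 < a + 12, that is a > 24 + d. With uniform entry over A months, the share is max(0, (A − 24 − d)/A). The documents give neither A nor d, so both are assumed.

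| Accrual A | d = 2 | d = 6 | d = 12 | d = 24 |
|---|---|---|---|---|
| 24 | 0 | 0 | 0 | 0 |
| 36 | 10/36 = 28% | 6/36 = 17% | 0 | 0 |
| 48 | 22/48 = 46% | 18/48 = 38% | 12/48 = 25% | 0 |
| 60 | 34/60 = 57% | 30/60 = 50% | 24/60 = 40% | 12/60 = 20% |

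A = 60 is what a trial of about 6 years that closes 1 year after last enrolment implies (72 − 12 = 60). If the first call falls 3 months after surveillance ends, the last row drops by 3/60 = 5 percentage points. The last-enrolled subject (a = 0) never reaches the calls: at least 36 months are needed and 12 are available.

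**3. Study end against the stated durations**

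The figure of about 6 years per subject can be reproduced: 36 months of treatment (the maximum in one sentence of Section 1) + 36 months of surveillance = 72 months. That is a maximum, while Section 1 calls it an average. With the 2-year treatment limit, also in Section 1, the sum is 24 + 36 = 60 months, or 5 years. Under the study-end definition, mean time from entry to study end is A/2 + 12 months. At A = 60 this is 42 months, or 3.5 years. The definition, the 3-year surveillance and the 6-year participation cannot all hold.

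**4. Sensitivity of overall survival**

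Simulation assumptions: exponential survival with true median 12 months, median 3 months to last dose, 24-month uniform accrual, and study end 12 months after accrual. A share f of deaths after the last dose is never learned of and is censored at the last 4-monthly visit, the 30-day call or the last dose.

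| f | KM median (months) | KM survival at 12 months |
|---|---|---|
| 0 | 12.0 | 50% |
| 10% | about 12.8 | about 52% |
| 20% | about 13.8 | about 54% |
| 30% | about 15.0 | about 57% |

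With a median of 6 months to last dose, the medians are about 12.5, 13.1 and 14.0 months. With a true median of 18 months, f = 20% gives about 21 months. At f = 0 there is no bias.

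**The case against.** The best defence is that the text never limits survival data to subjects who attend. Its stated aim is to learn the status of all subjects, and Section 5.8 requires documented attempts, by telephone or registered letter, to reach those who stop early or are lost. A competent site would ring a subject who missed a visit. Overall survival is also descriptive here: it has no hypothesis test and plays no part in the decision to open Stage 2.

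Much of this stands. A reader might infer that status is recorded only at attended visits. The documents do not say so, and taken literally that would mean no death could be recorded during surveillance. What is missing is any procedure for a missed visit. A reader might also infer that the study will usually be over before the calls begin. That depends on an unstated accrual time and on one side of a conflict in the durations; at 60 months of accrual, up to 57% of subjects reach the calls. Nor is overstated survival an established result, because it requires deaths to be missed in practice. Finally, a reader might extend the point to PFS and say that the month-4 visit is the only contact before the 6-month landmark. The imaging footnote in Section 6.1 continues tumour imaging throughout study participation, so that is not shown.

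The defence does not remove the gap. The duty in Section 5.8 is linked to end-of-therapy assessments and sets no recurring survival check. An aim of covering all subjects is not a means of reaching those who do not come.

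**Conclusion.** The point holds as a weakness in the follow-up schedule. For 36 months after the last dose, scheduled survival contact rests on nine surveillance visits, with no named contact for subjects who miss or decline them. Under the stated study end, the later calls reach nobody if accrual takes 24 months or less, and about 20–57% of subjects at 60 months (last dose 2 to 24 months after entry).

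Any bias would be upward. Its size rests on the missed share, which is unknown: in the main illustration, missing 10 to 30% of post-treatment deaths adds about 0.8 to 3.0 months to a true median of 12. These are sensitivity figures, not a forecast. Separately, and without any assumption about missed deaths, the study-end definition conflicts with the 3-year surveillance and the participation of about 6 years. Because overall survival is secondary and descriptive, this is a cheap improvement rather than a threat to the primary analysis.

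**What to change.** - In Section 2, Section 6.1 footnote 5 and Section 7.1.6.4, start the planned 3-monthly survival contact at the last ADXS11-001 dose for every subject, whether or not surveillance visits are attended. Accept status from family, the treating physician or records.
- At each data cut, check survival status for all subjects. Define overall survival and censor it at the last date known alive, in Section 8.3.1 or the SAP.
- Reconcile the end-of-study definition in Sections 1 and 2 with the 3-year surveillance and the stated durations of participation.

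This gives 36/3 = 12 scheduled contacts in the surveillance years, alongside the 9 visits. Even if the study end stays as written, the last-enrolled subject gets a call when d + 3 ≤ 12, that is when the last dose falls within 9 months of entry.

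The cost is about four short calls per subject per year, of a kind already planned, plus edits to three places and a short statistical definition. Treatment and safety monitoring rules do not change. The overall survival estimate may come out less favourable.

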3 OBJECTIVES & HYPOTHESIS

3.1 Primary Objectives & Hypothesis

Objective: To evaluate efficacy as measured by the overall response rate and rate of 6 month PFS in subjects with persistent/recurrent, loco-regional or metastatic SCCA of the anorectal canal as determined by RECIST 1.1

- a. **Hypothesis:** ADXS11-001 will produce response rates $\geq 10\%$ or 6 month PFS rates $\geq 20\%$ in subjects with persistent/recurrent, loco-regional or metastatic SCCA of the anorectal canal.
-

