8.2 Sample Size and the Design

This is a multi-center, open-label, 2 stage monotherapy study of ADXS11-001 in subjects with persistent/recurrent, loco-regional or metastatic SCCA of the anorectal canal that was previously treated in the metastatic setting.

Primary Efficacy Measures are:

1. The overall response
2. Progression-Free Survival (PFS)

We employed a 2-stage design for testing these 2 primary efficacy measures. Simon's 2-stage method is not directly applicable because it is for single proportion type endpoint. However, we used Simon's method with null and alternative response rates of 10% in Stage 1 and 20% in Stage 2 to obtain the total sample sizes for both stages and use the Multinomial Two-Stage approach proposed by Benny Zee, *et al* (1999) [24] to obtain the stopping probabilities.

By Simon's method, we need to enroll 31 subjects at Stage 1 and an additional 24 subjects in Stage 2 if 3 or more responses are observed in Stage 1. Based on this sample size plan, we formed the following 2 endpoints, 2-stage framework:

In Stage 1 of the study, we will enroll 31 subjects. The safety and efficacy data of the subjects will be evaluated. After 31 evaluable subjects have been enrolled, further accrual will be temporarily stopped in Stage 1 for an efficacy interim analysis evaluation. If the efficacy from Stage 1 demonstrates a response rate $\geq 10\%$ or 6-month PFS $\geq 20\%$,

the enrollment will re-open to Stage 2. The enrollment will be complete in Stage 2 when an additional 24 evaluable have been accrued (total from Stages 1 and 2 = 55).

The hypothesis testing in Stage 1 is given in the following:

- Stage 1:
 - Null Hypothesis (H_0): Response rates (r_1) <10% and 6-month PFS rate (p_1) <20%;
 - Alternative Hypothesis (H_a): Response rates (r_1) \geq 10% or 6-month PFS rate (p_1) \geq 20%
- Stage 2:
 - Null Hypothesis (H_0): Response rates (r_2) \leq 25% and 6-month PFS rate (p_2) \leq 50%;
 - Alternative Hypothesis (H_a): Response rates (r_2) \geq 25% or 6-month PFS rate (p_2) \geq 50%

Using the Multinomial Two-Stage approach proposed by Benny Zee, *et al* (1999),[\[24\]](#) we simulated 50,000 trials to examine the Type I and II errors under this design assumption. The following estimates, including Type I and II errors, from these simulations are summarized in the following table.

Type I	Type II
Type I Error = 0.03236 ASN for H0 = 32.20192 P(stop early H0) = 0.94992	Power = 0.924

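### Section 3.1 gives the Stage 2 opening thresholds (10%/20%) as the primary hypothesis, Section 8.2 sets a different Stage 2 hypothesis (25%/50%), and no final rule says which pair decides success

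*Combined protocol and SAP*

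**What the plan says.** Section 3.1, the only place where a hypothesis is attached to the primary objective, reads "ADXS11-001 will produce response rates $\geq 10\%$ or 6 month PFS rates $\geq 20\%$ in subjects". It names no stage and does not mention 25% or 50%.

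Section 2 gives the same pair another job, as the condition for re-opening enrolment after 31 evaluable subjects: "If the efficacy from Stage 1 demonstrates a response rate $\geq 10\%$ by either RECIST 1.1 or 6-month progression free survival (PFS) rate $\geq 20" (per cent).

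Section 8.2 builds Stage 1 on that pair, with the null "Response rates (r_1) <10% and 6-month PFS rate (p_1) <20" (per cent). It then gives Stage 2 its own pair: null "Response rates (r_2) \leq 25% and 6-month PFS rate (p_2) \leq 50" (per cent) against alternative "Response rates (r_2) \geq 25% or 6-month PFS rate (p_2) \geq 50" (per cent). It prints one set of operating characteristics, including "Type I Error = 0.03236" and a power of 0.924, without saying which final decision rule they describe.

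Section 2 plans the efficacy analysis on Stage 1 alone (interim) and on both stages combined. Section 8.3.1 plans tabulated response rates and Kaplan-Meier medians for PFS, and names no success threshold.

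**The concern.** Two threshold pairs compete for the same final analysis. The easier one is labelled the primary hypothesis, although elsewhere it serves only to let the trial continue. It also sits on the edge of the Stage 1 null, so observing a rate at or just above it is weak evidence against that null.

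In an open-label, single-arm trial, the success criterion fixed in advance is the main protection against choosing the favourable reading once the data are known. With no stage label in Section 3.1 and no final counts in Section 8.2, one dataset could be reported as confirming the primary hypothesis and also as falling short of the Stage 2 hypothesis. A reader could not tell which statement carries the printed error rates.

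**Working it through.** **Inputs.** From Section 8.2: 31 subjects in Stage 1, 24 in Stage 2, 55 in total; gate 10% or 20%; Stage 2 pair 25% or 50%; printed Type I error 0.03236, early stopping under the null 0.94992, expected sample size 32.20192, power 0.924. Assumed here: the true rates, and two extremes for the link between endpoints. *Nested* means every responder is also progression-free at 6 months. *Independent* means no link.

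**1. The plan's own figures.** The expected sample size agrees with the stopping probability: 31 + 24 × (1 − 0.94992) = 32.20192. The rest does not follow from the printed thresholds.
- The gate in counts is 0.10 × 31 = 3.1, so 4 responses, or 0.20 × 31 = 6.2, so 7 PFS successes. At true rates of 10%/20%, early stopping is then 0.36 (independent) to 0.47 (nested), not 0.95.
- Section 8.2 also says "we need to enroll 31 subjects at Stage 1 and an additional 24 subjects in Stage 2 if 3 or more responses are observed", and 3/31 = 9.7% is below 10%. Both gates are therefore carried below.
- The sizing text says "we used Simon's method with null and alternative response rates of 10% in Stage 1 and 20% in Stage 2". Yet 31/55 is the exact Simon minimax design for 10% versus 25% (continue at 4 or more of 31, success at 10 or more of 55, alpha 0.0422, power 0.9006).

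The printed figures therefore cannot be used to work out which final rule was meant.

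**2. Counts at n = 55, reading each pair as an observed-rate bar.**
- Section 3.1: 0.10 × 55 = 5.5, so 6 responses; or 0.20 × 55 = 11 PFS successes.
- Section 8.2, Stage 2: 0.25 × 55 = 13.75, so 14 responses; or 0.50 × 55 = 27.5, so 28 PFS successes.

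Conflict region: 6–13 responses or 11–27 PFS successes, with neither 14 nor 28 reached. If Stage 2 were judged on its own 24 subjects, the bars would be 3 or 5 against 6 or 12, and a conflict region remains.

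**3. Two example datasets (exact one-sided binomial p-values).**
- 8/55 (14.5%) and 15/55 (27.3%): above 10% and 20%, but p = 0.18 and 0.12 against those rates, and below 25% and 50%.
- 12/55 (21.8%) and 20/55 (36.4%): p = 0.0073 against 10% and 0.0036 against 20%, but p = 0.75 against 25% and 0.985 against 50%. Here the two pairs disagree under formal tests as well.

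**4. How often.** The probability is the sum, over Stage 1 results that pass the gate, of P(Stage 1 result) × P(the combined total reaches either count).

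| True rates | Gate (of 31) | Rule (of 55) | Nested | Independent |
|---|---|---|---|---|
| 9.99%/19.99% | 4 or 7 | 6 or 11 | 0.47 | 0.59 |
| 9.99%/19.99% | 3 or 7 | 6 or 11 | 0.55 | 0.67 |
| 10%/20% | 4 or 7 | 14 or 28 | 0.0008 | 0.0008 |
| 25%/50% | 4 or 7 | 14 or 28 | 0.66 | 0.76 |
| 10%/20% | 4 or 7 | 11 or 18 (illustration) | 0.031 | 0.036 |

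Meeting 14 or 28 implies meeting 6 or 11, so the probability of disagreement is the difference between the two rules. With the 4-or-7 gate it is 0.86–0.93 at true rates of 15%/30% and 0.75–0.77 at 20%/40%.

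**The case against.** The strongest reply is that Section 8.2 states hypotheses about true rates and gives no critical values. The 14-or-28 bar is then a construction, and no passage classes 8/55 and 15/55 as a failure. This stands: the conflict counts and the 47–59% depend on reading the hypotheses as observed-rate bars. An observed rate lands at or above its true value roughly half the time, so those percentages describe that reading and nothing more.

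A reader might also infer that a 10%/20% hypothesis cannot carry a 3.2% error rate. The documents do not support that. With stricter final counts, such as the illustrative 11 or 18 of 55, a 10%/20% null gives 3.1–3.6%. What is missing is the critical region.

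Sections 2 and 8.2 do make the gate role of 10%/20% clear, Section 8.1 speaks of descriptive statistics and leaves detail to the SAP, and nothing attaches 0.03236 to Section 3.1. These points limit the concern but do not remove it. Section 3.1 still presents the gate as the primary hypothesis, and no text in the combined document says which pair decides the primary objective.

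**Conclusion.** The inconsistency is real and the decision threshold is wrong as written: one primary objective, two threshold pairs, no stage label in Section 3.1 and no final rejection counts anywhere. That finding rests on the text alone. Its size rests on assumptions: the observed-rate reading, the choice of gate, and the dependence between endpoints. Under them, the Section 3.1 bar is met in 47–59% of trials just inside the Stage 1 null (55–67% with the gate of 3), and the two bars disagree in most trials at 15%/30% and 20%/40%.

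A reader might infer that 25%/50% is the correct final rule and that the printed error rates belong to it. The documents do not support either step. An observed-rate rule at 25%/50% has a Type I error of about 0.001 and power of 0.66–0.76, against the printed 0.03236 and 0.924. The match of 31/55 with a 10% versus 25% Simon design suggests that 10%/20% were meant as null rates and 25%/50% as targets, with success somewhere between. That is inference, and only the sponsor can settle it. Nor do the documents show any intention to claim success on the easier bar; the point is that the text would allow it.

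**What to change.** 1. In Section 3.1, label 10%/20% as the rule for opening Stage 2 only, and say that meeting it supports no efficacy claim.
2. State one final success rule, with explicit counts at n = 55 for response and for 6-month PFS, in the same words in Sections 2, 3.1 and 8.2. Say which rates are null and which are target.
3. Settle the Stage 1 response gate (3 or 4 of 31), since the error rates depend on it.
4. Recompute Type I error, early stopping and power for that rule, stating the assumed dependence between the two endpoints, and replace the printed 0.03236 and 0.924.

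Cost: wording in three sections and one recalculation, before the final analysis; no new patients, visits or data. The sponsor gives up the easier claim, and the restated error rates may look less favourable than those now printed.
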